#### Statistical analysis

The dichotomous variables will be expressed as numbers and percentages, while continuous variables will be expressed as mean and SD, or median and IQR (minimum and maximum values). Student's t test or ANOVA will be used for comparisons of continuous variables between groups. Chi-squared test or Fisher's exact test, as appropriate, will be used for analysis of categorical data. Multilogistic

regression models will be used to investigate clinical attitudes, physical, laboratory, and radiologic variables predictive of morbidity and mortality. A value of P < 0.05 will be considered statistically significant.

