#### **COVID-19 and management of AP**

In 2020, the spread of the virus Covid-19 had represented a pandemic, which also profoundly impacted the surgical community [24, 25]. The constant increase in the number of patients requiring treatment has represented a massive challenge for many involved countries' healthcare systems and could be their breaking point. In an emergency situation, resources must be concentrated and used rationally to handle the pandemic and continue handling the pre-existing diseases. In this context, most surgical departments were forced to re-schedule their activity, giving priority to urgent/emergent surgical cases and non-deferrable oncological cases. There are many ways the outbreak of the Covid-19 pandemic could have influenced daily clinical practice for patients with biliary AP, leading to a failure to adhere to the recommendations coming from the guidelines, especially those regarding the early and definitive treatment with cholecystectomy or ERCP and sphincterotomy. First of all, the recommendation to postpone all non-urgent endoscopic procedures during the peak of the pandemic. Second, the recommendation to conservatively treat inflammatory conditions such as acute cholecystitis and acute appendicitis wherever possible.

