#### Aim of the study

Since the clinical compliance with recommendations about AP is poor and the impact of implementing guideline recommendations in biliary AP has not been well studied globally, we launched the MANCTRA-1 study intending to demonstrate areas where there is currently a sub-optimal implementation of current guidelines on biliary AP.

Moreover, we argue that during the Covid-19 pandemic, the tendency to disregard the guidelines recommendations has been more marked than usual, and we will try to find out if AP patients' care during the Covid-19 pandemic resulted in a higher rate of adverse outcomes compared to non-pandemic times due to the lack in the compliance of the guidelines.

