#### Primary objective

! To evaluate which items of the current AP guidelines, if disregarded, correlate with

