# negative clinical outcomes according to the different clinical presentations of the disease

#### Secondary objectives

- ! To assess the compliance of surgeons worldwide to the most up-to-date international guidelines on biliary AP
- ! To evaluate the medical and surgical practice in the management of biliary AP during the nonpandemic (2019) and pandemic Covid-19 periods (2020)
- ! To investigate outcomes of patients with biliary AP treatment during the two study periods

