#### **Primary outcomes**

- ! 30-day mortality: assessed by the number of AP patients with biliary etiology deceased during the non-pandemic period (2019) and the Covid-19 pandemic period (2020)
- ! 30-day morbidity: assessed by the number of AP patients with biliary etiology who experienced any type of AP-related complication within 30-days from the hospital admission during the non-pandemic period (2019) and the Covid-19 pandemic period (2020)

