#### Secondary outcomes

- ! Early definitive treatment rate in 2019 vs. 2020: defined as treatment in accordance with the current guidelines (cholecystectomy or ERCP with endoscopic sphincterotomy during the same hospital admission or within 2 weeks of discharge)
- ! 30-day hospital readmission rate in 2019 vs. 2020: defined as hospital readmission within 30days from discharge for recurrent biliary AP while awaiting interval cholecystectomy, or due to post-cholecystectomy complications
- ! Predictive factors of morbidity and mortality in patients with biliary AP

The compliance of surgeons to the most up-to-date international guidelines on biliary AP will be assessed through the analysis of the following attitudes:

! Use of scoring systems for the diagnosis and severity grading of biliary AP

- ! Use of lipase dosage (for the diagnosis) and CRP (for the severity grading) during the diagnostic workup
- ! Use of Ultrasound scan, CT scan, MRCP, and endoscopic Ultrasound scan (EUS) in the correct way and timing
- ! Use of early ERCP and sphincterotomy in case of cholangitis and/or choledocholithiasis
- ! Use of percutaneous and/or endoscopic drainage in case of infected pseudocyst or necrosis
- ! Timing of surgical necrosectomy
- ! Timing of re-laparotomy in case of open abdomen strategies
- ! Use of prophylactic antibiotics/antifungals
- ! Use of somatostatin analogs
- ! Use of early enteral feeding
- ! Use of early definitive treatment strategies, including cholecystectomy and/or ERCP and sphincterotomy

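### No adjusted 2019-versus-2020 analysis of 30-day mortality and morbidity is specified, and Covid-19 status has no stated role in that comparison

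*Combined protocol and SAP*

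**What the plan says.** Primary outcomes defines mortality as "assessed by the number of AP patients with biliary etiology deceased during the non-pandemic period (2019) and the Covid-19 pandemic period (2020"), and morbidity in the same way. Comparing outcomes between the years is a secondary objective: "To investigate outcomes of patients with biliary AP treatment during the two study periods". Aim of the study goes further and asks whether pandemic care "resulted in a higher rate of adverse outcomes compared to non-pandemic times due to the lack in the compliance of the guidelines". Sample size builds the 200 per group on whether changed care affected overall mortality.

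The analysis plan is one paragraph under Statistical analysis. For binary data it states "Chi-squared test or Fisher's exact test, as appropriate, will be used for analysis of categorical data". Its only multivariable sentence says that multilogistic "regression models will be used to investigate clinical attitudes, physical, laboratory, and radiologic variables predictive of morbidity and mortality". Secondary outcomes lists the matching item, "Predictive factors of morbidity and mortality in patients with biliary AP". None of these names period as a model term, gives a covariate set for the year contrast, or says what is done with Covid-19 status. None names a centre term.

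The data are on the CRF. Section 2 has year of admission, age, sex, previous episodes and Covid-19 status (negative, positive or untested). Section 3 has the Charlson index. Sections 5 and 6 have admission vital signs and laboratory tests.

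**The concern.** The year of admission is not randomised. If the patients admitted in 2020 had worse prognosis on arrival, or some had Covid-19, mortality and morbidity would rise with no change in how pancreatitis was managed. An unadjusted test cannot separate these explanations from changed care, yet the Aim and Sample size sections seek that attribution. The protocol itself makes the rivals plausible. The COVID-19 section says "most surgical departments were forced to re-schedule their activity, giving priority to urgent/emergent surgical cases and non-deferrable oncological cases", and the title of reference 25 links infection in acute pancreatitis to greater severity and 30-day mortality.

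At stake is the reading of the headline comparison: a case-mix or infection difference could be published as harm from disregarding guidelines. Tabulating compliance by year would show whether compliance changed, not whether it caused the difference.

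A lesser point concerns the primary objective, "To evaluate which items of the current AP guidelines, if disregarded, correlate with" negative outcomes. Hospitals may differ both in practice and in baseline risk, and the models for guideline items name nothing to separate the two.

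**Working it through.** **1. The plan's own figure.** Sample size gives 200 per group, power 0.80, one-sided 5%, and mortality of about 10%. It states no 2020 mortality, so 200 cannot be derived. Solving n = (1.645 + 0.842)² × [0.10 × 0.90 + p(1 − p)] / (p − 0.10)² for n = 200 gives p of about 18.6%. The calculation is for two crude proportions, with no covariates. The 95% half-width for a difference near 10% is 1.96 × √(2 × 0.09/200) = 5.9 points.

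**2. Case-mix shift (assumed).** Three admission covariates, each with log odds ratio 0.6 per SD, are each 0.1 or 0.2 SD worse in 2020. There is no period effect and 2019 mortality is 10%. Averaging the logistic risk over the covariates gives 2020 mortality of 11.55% or 13.3%. The crude odds ratios are (0.1155/0.8845)/(0.10/0.90) = 1.18 and (0.133/0.867)/(0.10/0.90) = 1.38.

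**3. Covid-19 (assumed).** 2020 mortality = 0.10 × (1 − q + q × RR). With q = 5% and RR = 2 it is 10.5%; with q = 15% and RR = 3 it is 13.0%.

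**4. Severe share (Sample size rates, assumed rise).** Severe mortality is 30% in 20% of patients, and 10% overall implies (0.10 − 0.20 × 0.30)/0.80 = 5% in the rest. A severe share of 25% gives 0.25 × 0.30 + 0.75 × 0.05 = 11.25%; 30% gives 12.5%. Part of such a rise could itself reflect care.

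**5. Rejection by the crude test.** Exact enumeration of two binomials, 10% in 2019, 200 per year:

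| 2020 mortality | Chi-squared, two-sided 5% | Fisher | One-sided 5% |
|---|---|---|---|
| 10% (no shift) | 4.8% | 3.4% | 5.0% |
| 10.5% | 5.1% | 3.6% | 6.9% |
| 11.25% | 6.7% | 4.9% | 10.8% |
| 11.55% | 7.7% | 5.7% | 12.6% |
| 12.5% | 12.1% | 9.4% | 19.7% |
| 13.0% | 15.3% | 12.1% | 24.2% |
| 13.3% | 17.3% | 13.9% | 26.9% |

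At an assumed 1,000 per year, the two case-mix shifts give chi-squared rejection of 20% and 63%. For morbidity at an assumed 20% to 40% and 200 per year, the same shifts give 9% to 11% and 25% to 30%.

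**6. Adjusted model.** In simulation at 200 per year, a logistic model with period and the three covariates returns a period odds ratio of about 1.0 and rejects in 5.2% (0.1 SD) and 4.5% (0.2 SD) of studies. This is the favourable case, since the model contains exactly the covariates that shifted. With covariates measured at reliability 0.7, the odds ratio stays at 1.05 to 1.11 and rejection at 5% to 7%.

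**7. Untested patients.** Suppose 2020 mortality is 10%, 30% are untested, and the untested have 5% mortality. Tested patients then have (0.10 − 0.30 × 0.05)/0.70 = 12.1%, so dropping the untested creates a 2.1-point artefact. Now suppose instead that testing is unrelated to risk, 10% are infected, RR is 2.5 and 30% are untested. Crude mortality is 11.5%. Removing known positives but keeping the untested gives (0.30 × 0.115 + 0.63 × 0.10)/0.93 = 10.5%. Dropping the untested as well would leave 200 × 0.70 × 0.90 = 126 patients.

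**8. Centre (assumed).** Item with no effect, outcome ICC 0.05, item ICC 0.2, practice-risk correlation 0.3 to 0.5, one patient covariate in the model. False positives with 40 centres of 10 patients (the planned 400) are 6% to 7% if the covariate captures none of the centre risk, and about 6% if it captures half. With 100 centres of 50 they are 14% to 33% and 7% to 12%. At the planned 400, clustered standard errors alone leave the first figure at 6% to 7%; a centre-mean term with clustered errors brings all scenarios to 3.6% to 6.3%.

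**The case against.** **Softer aims.** The primary objective speaks of correlation, the secondary objective of investigating outcomes, and the primary outcomes are counts by year. For description, a crude test is adequate. This stands as far as it goes, and is why the crude comparison should stay. It does not cover the attribution sought in Aim of the study and Sample size.

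**Covid-19 status.** A reader might infer that it is ignored altogether. The documents do not support that. The CRF is headed as analysed data, Study population says demographic and comorbidity data will be evaluated, and the predictive-factors outcome is not restricted by variable type. Tables by year would probably show an imbalance. What is missing is a specified role in the period comparison.

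**Different patients.** A reader might also infer that the protocol says 2020 pancreatitis patients were different. It says departments re-scheduled their activity, and uses this to explain lower adherence. A change in the patients admitted is a reasonable inference, not a stated fact.

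**Size.** Every shift is assumed, the main scenario moves three covariates in the same adverse direction, and 1.6 to 3.3 points is small beside a half-width of 5.9. This stands for mortality at 200 per year. But 200 is a minimum in a multicentre study of all consecutive patients, and larger numbers do not reduce the bias.

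**Adjustment can mislead.** Admission markers may already carry the effect of late presentation or infection, and dropping untested patients can bias. Both stand and shape the fix.

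**Conclusion.** The omission is real and should be corrected. The plan specifies no adjusted analysis of its two primary outcomes by year, and no use of Covid-19 status in that comparison. That the comparison would be a chi-squared or Fisher test is an inference: no sentence assigns a test, but no other named method fits. Such a result could not support the attribution to compliance or changed care.

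The size rests wholly on assumptions. For mortality it is modest at 200 per year (about 8% to 17% rejection where 5% is nominal) and becomes serious only with larger enrolment (20% to 63% at an assumed 1,000). It would be wrong to conclude that a 2020 difference will be spurious, or that adjustment would settle causation.

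The centre point is minor: at the planned 400 the assumed scenarios give about 6% to 7% false positives at most.

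**What to change.** - **Main period analysis.** Keep the crude comparison as descriptive. For each primary outcome, prespecify a logistic model with period as exposure, adjusted for age, sex and Charlson index, plus previous episodes if events allow. State the target as the total period effect. Report the adjusted odds ratio and a standardised risk difference.
- **Sensitivity analyses.** (a) Add one admission vital sign or laboratory marker, noting that it may lie on the path from late presentation or infection to outcome. (b) Exclude Covid-positive 2020 patients and keep untested ones. An analysis that also drops untested patients is exploratory only, since testing may have followed severity.
- **Interpretation.** Report the period difference as an association, not as due to non-compliance.
- **Guideline-item models.** Use centre-clustered standard errors, with centre taken from the Local Lead. For common items only, add a centre-mean compliance term as a sensitivity analysis; for rare items it is barely estimable at about 10 patients per centre.

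**Cost.** SAP wording and modest extra analysis; the period model's variables are already on the CRF. In simulation the period standard error rises 7% to 8% with four terms and 8% to 10% with seven, at 200 per year. About 0.10 × 400 = 40 deaths allow few covariates. Confounding not captured by the chosen variables remains.

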#### Section 7 – Diagnostic Imaging

! Initial diagnostic imaging (Ultrasound scan on admission/CT scan on admission/CT scan <24h/CT scan 24-48h/CT scan >48h)

- ! MRCP (MRCP on admission/MRCP <24h/MRCP >24h/No)
- ! Endoscopic ultrasound scan (Yes <24 hours/Yes >24 hours/No)
- ! Re-evaluation with CT scan (None/<7 days/7-14 days/15-30 days/>30 days)

Section 8 – Physical examination on admission (Localized abdominal pain/Localized abdominal rigidity/Diffuse abdominal pain/Diffuse abdominal rigidity/No abdominal pain/No abdominal rigidity)

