## Section 10 – 30-day Morbidity

- ! Gastric outlet obstruction (Yes/No)
- ! Pseudocyst (Yes/No)
- ! Infected necrosis (Yes/No)
- ! Endoscopic drainage of pseudocyst/walled-off necrosis (Yes/No)
- ! CT-guided fine needle aspiration in case of infected pseudocyst/walled-off necrosis (Yes/No)
- ! Surgical necrosectomy (Yes-laparoscopic/Yes-open/No)
- ! Timing of surgical necrosectomy (< 2 weeks from the onset of symptoms/2-4 weeks)>4 weeks)
- ! Setting of surgical necrosectomy (Upfront/After failure of endoscopic necrosectomy/After failure of endoscopic and percutaneous necrosectomy)
- ! Cystogastrostomy (Yes-endoscopic/Yes-surgical/No)
- ! Abdominal compartment syndrome (Yes/No)
- ! Open abdomen (Yes/No)
- ! Timing of re-exploration (24-48 hours/48-72 hours/>72 hours)
- ! Bleeding (Yes/No)
- ! Bowel ischemia (Yes/No)

- ! Bowel fistula (Yes/No)
- ! Necrotizing cholecystitis (Yes/No)

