5. Risk scores	!	There are no "gold standard" prognostic score for predicting severe acute pancreatitis. Probably the bedside index of severity of acute pancreatitis (BISAP) score is one of the most accurate and applicable in everyday clinical practice because of the simplicity and the capability to predict severity, death, and organ failure as well as the APACHE-II (very complex) and other scores (1B).
6. Follow-up imaging	!	In severe acute pancreatitis (computed tomography severity index $\geq$ 3), a follow-up CECT scan is indicated 7–10 days from the initial CT scan (1C). Additional CE-CT scans are recommended only if clinical status deteriorates or fails to show continued improvement, or when invasive intervention is considered (1C).
7. Prophylactic antibiotics	!	Recent evidences have shown that prophylactic antibiotics in patients with acute pancreatitis are not associated with a significant decrease in mortality or morbidity. Thus, routine prophylactic antibiotics are no longer recommended for all patients with acute pancreatitis (1A).
8. Infected necrosis and antibiotics	! ! !	Antibiotics are always recommended to treat infected severe acute pancreatitis. However the diagnosis is challenging due to the clinical picture that cannot be distinguished from other infectious complications or from the inflammatory status caused by acute pancreatitis (2A). Serum measurements of procalcitonin (PCT) may be valuable in predicting the risk of developing infected pancreatic necrosis (1B). A CT-guided fine-needle aspiration (FNA) for Gram stain and culture can confirm an infected severe acute pancreatitis and drive antibiotic therapy but is no longer in routine use (1B).
9. Type of antibiotics	!	In patients with infected necrosis, antibiotics known to penetrate pancreatic necrosis should be used (1B). In patients with infected necrosis, the spectrum of empirical antibiotic regimen should include both aerobic and anaerobic Gram-negative and Gram-positive microorganisms. Routine prophylactic administration of antifungal is not recommended in patients with infected acute pancreatitis, although Candida spp. are common in patients with infected pancreatic necrosis and indicate patients with a higher risk of mortality (1B).

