	
 
accompanying an aggravated general condition. (1C)
 
! Infected pancreatic necrosis should be suspected when clinical symptoms and blood test findings deteriorate. Routine use of FNA is not required for diagnosis, and clinical signs and CT should be used for a comprehensive determination. If an aggravated general condition is observed, percutaneous drainage or endoscopic drainage should be given for diagnosis and treatment. (1C)
 
! If possible, therapeutic intervention for infected pancreatic necrosis should be performed after 4 weeks of onset, when the necrosis has been sufficiently walled off, or in other words, during WON period. (2C)
 
! During therapeutic intervention for infected pancreatic necrosis, percutaneous (retroperitoneal) drainage or endoscopic transluminal drainage should be first given, and if no improvement is achieved, necrosectomy should then be performed. Necrosectomy by endoscopic or retroperitoneal approach is recommended. (2B)
 

16. Post-ERCP pancreatitis	
 
Prophylactic temporary pancreatic stent placement is useful as an effective endoscopic procedure for the prevention of post-ERCP pancreatitis. This should only be performed in the high-risk groups for post-ERCP pancreatitis given the risks and cost. (2A)
 
The guidewire method is very likely to reduce the incidence of post-ERCP pancreatitis. (2A)
 
For the prevention of post-ERCP pancreatitis, the intrarectal administration of NSAIDs should be carried out for all cases undergoing ERCP with no contraindications. (2A)
 
(Other drugs should not be used as routine preventive measures, since their efficacy has been refuted or is uncertain.)
 

17. Clinical indicators (pancreatic bundles)	! A high rate of implementation of the pancreatitis bundles may contribute to improving prognosis of patients with severe acute pancreatitis. (1C)

From: Yokoe M, Takada T, Mayumi T, Yoshida M, Isaji S, Wada K, Itoi T, Sata N, Gabata T, Igarashi H, Kataoka K, Hirota M, Kadoya M, Kitamura N, Kimura Y, Kiriyama S, Shirai K, Hattori T, Takeda K, Takeyama Y, Hirota M, Sekimoto M, Shikata S, Arata S, Hirata K. Japanese guidelines for the management of acute pancreatitis: Japanese Guidelines 2015. J Hepatobiliary Pancreat Sci. 2015 Jun;22(6):405-32. doi: 10.1002/jhbp.259. Epub 2015 May 13. PMID: 25973947.

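### CT use is tested as a predictor of 30-day morbidity that is partly found by CT and partly prompts it, so CT items can show an association with no true effect

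*Combined protocol and SAP*

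**What the plan says.** The primary objective is "To evaluate which items of the current AP guidelines, if disregarded, correlate with" "negative clinical outcomes according to the different clinical presentations of the disease". The compliance attitudes listed under Secondary outcomes include "Use of Ultrasound scan, CT scan, MRCP, and endoscopic Ultrasound scan (EUS) in the correct way and timing"; what counts as correct is not defined. The only model in the Statistical analysis section is logistic: "regression models will be used to investigate clinical attitudes, physical, laboratory, and radiologic variables predictive of morbidity and mortality".

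Morbidity is a primary outcome and counts any AP-related complication in the 30 days after admission. CRF Section 10 lists pseudocyst and "Infected necrosis (Yes/No") among its items, with neither a date nor a method of detection. CRF Section 7 records "Re-evaluation with CT scan (None/<7 days/7-14 days/15-30 days/>30 days"), without the reason for the scan.

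The guideline tables show how CT relates to the clinical course:
- Table 1, item 6: "Additional CE-CT scans are recommended only if clinical status deteriorates or fails to show continued improvement". The same item also schedules a follow-up scan in severe disease 7 to 10 days after the first.
- Table 2, item 2 calls for CT when organ failure persists, sepsis is suspected or the patient worsens 6 to 10 days after admission.
- Table 4 (2015 Japanese guidelines), item 15, on infected necrosis: "clinical signs and CT should be used for a comprehensive determination".

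**The concern.** Two mechanisms link CT to recorded morbidity without any effect of CT on the patient.

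- **Detection.** A collection that nobody images is less likely to be entered as a complication, so unscanned patients have fewer recorded events.
- **Indication.** Repeat CT is advised in severe disease and on deterioration, so the complication, or its early signs, can cause the scan.

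The last category of the re-evaluation field lies beyond the 30-day window, so this predictor can be measured after the outcome. Even a purely predictive model cannot use such a variable.

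The study intends its findings on guideline items to support care bundles (The rationale for the study). A spurious coefficient on a CT item would feed into them. If CT use also changed between the two years, the 2019-versus-2020 morbidity comparison would carry the same detection bias.

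**Working it through.** The plan gives no figure for this point. Its one design number, 200 per year group, serves the mortality comparison, comes without an effect size and does not enter the bias. The inputs below are assumptions unless a source is named.

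**1. Detection alone, true odds ratio (OR) = 1.** Take a true risk of 20% in everyone, detection of 95% with CT and 50% (range 40% to 70%) without. Let f be the share of complications whose recording depends on CT; the rest are always recorded.

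Recorded risk = 0.20 × (f × detection + 1 − f).

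| f | With CT | Without CT | OR for no CT (range) |
|---|---|---|---|
| 1 | 19.0% | 10.0% | 0.47 (0.37 to 0.69) |
| 0.5 | 19.5% | 15.0% | 0.73 (0.67 to 0.85) |
| 0.25 | 19.75% | 17.5% | 0.86 (0.83 to 0.92) |

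Example, f = 1: (0.10/0.90) / (0.19/0.81) = 0.111/0.235 = 0.47. With equal detection in both groups the OR is 1.00.

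**2. How often this reaches P < 0.05.** Take an illustrative 200 scanned and 200 unscanned patients and a two-sided pooled two-proportion test. For f = 1 the pooled risk is 0.145. The null SE is √(2 × 0.145 × 0.855/200) = 0.0352, and the SE under the alternative is √((0.19 × 0.81 + 0.10 × 0.90)/200) = 0.0349. Power = Φ((0.09 − 1.96 × 0.0352)/0.0349) = Φ(0.60) = 73% (27% to 90% over the detection range). For f = 0.5 it is 22% (10% to 31%), and for f = 0.25 about 9%.

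**3. Indication alone, full detection.** Let c1 and c0 be the probability of CT with and without a complication. The OR for no CT is [(1 − c1)/c1] / [(1 − c0)/c0], whatever the risk. With c0 = 0.3 the denominator is 2.33. For c1 = 0.4, 0.6 and 0.8 the OR is 1.5/2.33 = 0.64, 0.667/2.33 = 0.29 and 0.25/2.33 = 0.11.

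**4. Direction by type of item.** If disregard means omitting a scan, the ORs above apply. If it means a scan that was not advised, the ratio inverts. From step 1 it becomes 1/0.474 = 2.11, 1/0.729 = 1.37 and 1/0.862 = 1.16, so disregard looks harmful.

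**5. Does severity adjustment remove it?** The formula in step 3 also holds within a severity stratum, so bias remains wherever scanning still responds to deterioration. In a simulation with 20% severe cases (Sample size section) and assumed scan and complication rates, CT was ordered on deterioration and 70% of complications were detected without CT. The null OR for no CT was 0.22 crude, 0.33 adjusted for severity and 0.62 adjusted for severity and deterioration. With full detection these were 0.33, 0.51 and 1.01. In samples of 400, severity-adjusted, 64% gave P < 0.05, all favouring no CT. I use this only to show that severity adjustment alone need not suffice.

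**The case against.** A reader might infer that disregarding imaging advice will look protective. The documents do not support that. Table 1, item 2 sets a window for the first contrast CT (72 to 96 hours from onset) and item 6 restricts further scans, so disregard can also mean an early or extra scan, for which the bias runs the other way. Compliance is not coded in the plan, so the net sign is open.

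A reader might also take all imaging items to be affected. Ultrasound, MRCP and endoscopic ultrasound appear in the tables mainly for cause of disease and bile duct stones, and nothing links their omission to missed collections. Table 4, item 15 concerns infected necrosis, so dependence of pseudocyst on imaging is plausible but not stated there.

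The largest figures (OR 0.47, 73% significant) treat all morbidity as dependent on CT. CRF Section 10 also lists events such as compartment syndrome and bowel fistula that need not be. The 200 versus 200 split is by calendar year; no CT split is given, and the ORs in steps 1 to 4 are crude whereas the plan uses regression.

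Severity is collected on the CRF, the primary objective mentions clinical presentation, and the aims speak of correlation and prediction. All this is fair and limits size, sign and scope. It does not supply a safeguard: the Statistical analysis section ties neither severity nor presentation to the models and leaves CT use among the predictors of morbidity.

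**Conclusion.** The point holds for CT items against morbidity. Followed as written, the analysis can return an association with no true effect: scanning looks harmful and not scanning looks safe. For omitted scans, detection bias alone gives a null OR of about 0.47, 0.73 or 0.86 as all, half or a quarter of complications depend on CT. Indication pushes the same way. These sizes rest on the assumed 20% risk and 95%/50% detection; the documents give none of these.

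Mortality is free of detection bias but not of confounding by indication. A reader might infer that the 2019-versus-2020 morbidity comparison is biased too. That holds only if CT use changed, and the protocol's COVID-19 section speaks of postponed endoscopy and conservative treatment, not of CT.

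**What to change.** Amend the Statistical analysis section as follows.

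1. Remove re-evaluation CT from the predictors of morbidity and mortality and report it descriptively.
2. Do not test initial-CT items against a composite that includes pseudocyst or infected necrosis. Test them on 30-day mortality and on morbidity without those components, and describe the results as associations only. Adjust for severity measured at admission, for example BISAP if scored then, vital signs and laboratory values, all on the CRF.
3. Code each CT item separately as an omitted, early or extra scan, within the severity group to which the advice applies.
4. Report 2019-versus-2020 morbidity with and without the imaging-detected components, and list those components in advance. Bleeding should not be assumed free of imaging, since Table 4, item 2 names CT for active haemorrhage. Organ failure is not a clean substitute outcome either, since Table 2 makes it a reason for CT.

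This needs no new data. The cost is fewer events for the CT items. Residual confounding by indication stays, because neither the reason for a scan nor the date of a complication is collected. Item 3 can only be approximate: the CRF does not time the first CT from symptom onset and has no explicit category for no initial CT.
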